# PARTNERS HUMAN RESEARCH COMMITTEE

## DETAILED PROTOCOL

### II. SPECIFIC AIMS

- 1) *To document changes in body composition (visceral adiposity) and insulin sensitivity (homeostatic model assessment) resulting from FES-RT in comparison to a time (wait-list) control and to arms-only row training (arms-only-RT)*

We hypothesize FES-RT will mitigate against increased visceral adiposity and reduced insulin sensitivity occurring with acute SCI and that FES-RT will be more effective than arms-only-RT.

- 2) *To quantify changes in key indices of cardiovascular health (serum lipids) and control (arterial baroreflex gain) with FES-RT in comparison to a time control and to arms-only-RT*

We hypothesize FES-RT will prevent the worsening lipid profile and compromised baroreflex function occurring with acute SCI and that FES-RT will be more effective than arms-only-RT.

- 3) *To characterize changes in myocardial structure (left ventricular wall thickness) and function (left ventricular diastolic velocity) with FES-RT in comparison to a time control and to arms-only-RT*

We hypothesize FES-RT will counter the ventricular wall thickening and declining ventricular function occurring with acute SCI and that FES-RT will be more effective than arms-only-RT.

- 4) *To compare the body composition, insulin sensitivity, cardiovascular health and control, and myocardial structure and function and the magnitude of adaptations to FES-RT across a range of injury duration from acute to chronic SCI.*

We hypothesize that cross-sectional declines in all variables will relate directly to injury duration and that therefore the magnitude of adaptations will be greater with longer injury duration.

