#### **2) ARMS-ONLY-RT GROUP(Acute SCI only)**

The arms-only-RT group will commence exercise training upon enrollment. Training sessions will be 3 times per week for 26 weeks. To parallel the FES-RT, the initial training sessions will also consist of 6 sets of arms-only rowing for five minutes at 60% of VO2peak with a work-to-rest ratio of 2:1 and progress over the six months to an exercise intensity of 75-85% maintained for 30 minutes performed three times each week. The arms-only-RT group will also perform the FES-leg strength training protocol as described above during their six months of arms-only training. During this time they will not use the FES-device on the rowing ergometer. Strengthening the leg muscles during the arms-only period will lessen leg muscle atrophy and allow faster progress in FES-row training when they enter that phase of the study. A maximum arms-only rowing test will be performed at baseline. This will be repeated after three months of training and training intensity will be adjusted to maintain the training stimulus at the same relative intensity. A maximum arms-only rowing test will be performed at the end of the six months of training to determine increases in fitness. Subsequently, after the six months of arms-only-RT, subjects will begin the FES-RT as described above.

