### **Study Assessments**

Most Assessments will be performed at baseline and after 3 and 6 months for each study group. The DXA measurements and the AO-VO2max test (for the FES-RT group only) will only be performed at baseline and after 6 months. The Arms-only-RT and Wait-list groups will immediately enter baseline FES-RT protocol after completing all study procedures required in their initial group. Their six month lab visit and DXA scan data will also be used as their baseline FES-RT measures. Subjects may be asked to repeat any of the study assessments if there is difficulty obtaining results that meet our quality standards or there are equipment issues that arise.

Subjects that take longer than eight weeks to progress to performing their baseline FES-VO2max test will perform an extra assessment around the time of their baseline FES-VO2max test to account for changes that may occur over that time period. This extra study session will consist of: height, weight and circumference measures, blood samples, health questionnaires, pulmonary function tests, resting cardiovascular hemodynamics and neck suction-baroreflex testing. This extra testing session will take about 2-hours and can be done on a normal training day.

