## VI. BIOSTATISTICAL ANALYSIS

Power analysis: Based on longitudinal exercise capacity data from our lab, extensive sets of power analyses were performed. For the main analysis (acute subjects only), there will be 3 groups of subjects (FES-RT, wait-list and arms-only-RT) and measures at baseline, 3 months, 6 months, except for visceral adiposity (only at baseline and 6 months). The primary analysis (below) will include the three groups and will have as predictors two indicator (dummy) variables for two of the groups, and indicators for the 3 month and 6 month time points and interactions between the time points and the group indicator variables; this will be estimated as a linear mixed model. The only random effect will be for subject. In addition, for the fourth aim, the analysis will only include those entered into FES-RT at the outset, i.e., the FES-RT with acute SCI and all

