*Primary data analysis:* The primary analysis will test whether the FES-RT has 'better' values of the outcome variables at 6 months post-baseline. A general linear mixed model with a random effect for subjects will be used to conduct an intent-to-treat analysis. The main predictors will be indicator variables for group with the FES-RT group as the reference group and indicators for each of the other two groups, the time at which the outcomes were measured and treatment group by time interactions; menstrual status (with men coded the same as women who are not menstruating) will be included as a dummy variable; for the insulin resistance measure, body weight/fat changes will be included as a predictor. In a secondary analysis, we will include interactions terms between the group indicators and the 3 month indicator. In addition, similar models to the above will be estimated for secondary outcomes.

*Checking and Sensitivity Analyses:* It is important to ensure that data idiosyncrasies do not impact the results and that the results are generalizable. We will check for systematic differences between the model and the data using graphs, such as comparisons of predicted and observed values of the outcome variable, and other standard diagnostics. An extension of this idea is to simulate new sets of data based on our model and use the simulated data as a reference test group by comparing this to the observed data; we do this to look for situations in which the data appear different

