## PARTNERS HUMAN RESEARCH COMMITTEE

### DETAILED PROTOCOL

from what we would expect by using the model to predict the data. We will also check whether any important predictors have been left out of the model, for example, gender or severity of SCI or level of SCI. These will be tested by including them in revised versions of the model and testing whether the model is substantively improved. It is also important to explore the ‘missingness’ of data. The model we plan to use assumes that missing data are “missing at random.” This can be checked in several ways including comparing the characteristics of observations with and without missing values. More importantly, we can check whether our results would change if the data is “missing not at random” in several ways. For certain outcome variables, it may be the case that subjects who are either at the high end or the low end are more likely to be missing. For example, people at baseline who are very fat or very lean may be more likely to drop out. This can be checked by using constrained multiple imputation where we constrain our imputations to one end of the adiposity range. Comparing the results based on the constrained imputation to the unimputed results gives us a sensitivity analysis.

A second type of sensitivity analysis was originally suggested by Rubin and has been extended by Carpenter, Kenward and White who suggest weighting each imputed result (rather than Rubin’s standard “rules” of averaging the results), where the weight depends on the assumed departure from the MAR assumption. This technique relies on the imputations covering a fairly wide range of values (we would use 100 imputations) but this can be checked and additional data sets imputed if the range is too narrow. Carpenter, *et al.*, provide a graphic method of checking whether the range is wide enough. Finally, if dropouts are much more common than missing an occasion and then returning, we will estimate a pattern-mixture model. However, if there are many people who miss the 3 month measure, but not the 6 month measure, we will not pursue this strategy. A fourth issue deals with the variance structure of the model. Our prime model assumes that the variances are the same across groups. This will be tested by estimating a model with heterogeneous variance structures by group (this is available in some statistical packages, including Stata or SAS).

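### The primary insulin-resistance model adjusts for post-randomisation change in weight or fat, with no stated coding, so it may not estimate the effect Aim 1 asks about

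*Combined protocol and SAP*

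**What the plan says.** Section VI, Primary data analysis, sets out an intent-to-treat linear mixed model with a random subject effect, FES-RT as the reference group, and group, time and group-by-time terms. The test is whether FES-RT has better "values of the outcome variables at 6 months post-baseline". For one outcome a further term is added: "for the insulin resistance measure, body weight/fat changes will be included as a predictor". Nothing more is said about it: not the measure, the interval, whether it takes one value per subject or per visit, or whether it interacts with time.

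Section II, Aim 1, names visceral adiposity and insulin sensitivity as outcomes side by side: "We hypothesize FES-RT will mitigate against increased visceral adiposity and reduced insulin sensitivity occurring with acute SCI".

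The power paragraph of Section VI lists the primary-model predictors, including "interactions between the time points and the group indicator variables", without any weight or fat term, but points forward to the primary analysis text.

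On timing, Section V (Study Assessments) says: "The DXA measurements and the AO-VO2max test (for the FES-RT group only) will only be performed at baseline and after 6 months". Weight belongs to the lab visits, which the time line places at baseline, 3 and 6 months.

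Under Checking and Sensitivity Analyses the predictor check works in one direction only: "We will also check whether any important predictors have been left out of the model". Its examples are gender and the severity and level of injury. The other checks concern model fit, missing data and group variances.

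**The concern.** Aim 1 asks what FES-RT does to insulin sensitivity, not what it does at a fixed change in weight or fat. Conditioning on a variable that treatment may itself change alters the question. On the trial's own hypothesis, fat is such a variable; that treatment changes weight is an inference, not a stated hypothesis.

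Two things can go wrong. The part of the effect that runs through weight or fat can be removed from the estimate. And if unmeasured factors drive both fat change and insulin change, adjustment can create a group difference where none exists.

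Whether either happens depends on a coding the plan does not state. That leaves a decisive choice to be made at analysis, possibly with the data in hand, for a primary intent-to-treat test. No planned model without the term would reveal the difference.

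**Working it through.** **1. The plan's own figures.** 60 recruited to give 50 is 1 − 50/60 = 16.7% loss, against about 15% stated; 50/0.85 = 58.8, or 59, against 60. 50 × 40/30/30% = 20/15/15, which agrees with 1.33:1:1. These reproduce closely but do not bear on the concern. Power cannot be reproduced, because no power value, effect size or SD is given for the three-group comparison. Section III gives other group sizes (25, 18, 17); the Section VI sizes are used below.

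**2. Inputs.** From Section VI: 20/15/15, baseline-to-6-month correlation 0.7, alpha 0.05. Assumed: outcome SD 1; total effect 0.76 SD at 6 months and half that at 3 months; two-sided test; complete data; within-arm SD of fat change 1; *a* = arm effect on fat change in those SDs. Positive differences favour FES-RT.

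- SD of change = √(2 × (1 − 0.7)) = √0.6 = 0.775.
- SE, FES-RT against one comparator = 0.775 × √(1/20 + 1/15) = 0.265.
- Unadjusted power ≈ Φ(0.76/0.265 − 1.96) = Φ(0.91) = 82%.

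The mixed model was then simulated with visits at 0, 3 and 6 months, 3,000 runs per setting.

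**3. One value per visit.** Expected group-by-6-month coefficient = 0.76 × (1 − mediated share).

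| Mediated share | *a* | Expected | Simulated | Power without term | Power with term |
|---|---|---|---|---|---|
| 0% | 0.4 to 0.8 | 0.76 | 0.75–0.76 | 81–83% | 77–81% |
| 10% | 0.2 | 0.68 | 0.68–0.69 | 77–84% | 73–82% |
| 25% | 0.4 | 0.57 | 0.57–0.58 | 75–87% | 57–76% |
| 25% | 0.8 | 0.57 | 0.56 | 80–83% | 53–56% |
| 50% | 0.8 | 0.38 | 0.38 | 74–86% | 27–42% |

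The power ranges cover two treatments of the mediated variance: variance of change held at 0.6, or mediated variance added to it. When it is held, the share cannot exceed *a* × 0.775/0.76, which is 20% at *a* = 0.2 and 41% at *a* = 0.4.

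A second set of assumptions (total effect 0.75 SD, slope of outcome on fat change 0.5, residual SD of fat change 0.5) gave 0.56 SD at 25% and 0.37 SD at 50%, with power 49% and 21% against about 75% unadjusted.

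**4. Visit schedule and interaction terms.** With baseline and 6 months only, as DXA is scheduled, the coefficients are 0.57 (25%) and 0.385 (50%), so the loss is the same. If the primary model holds only the 6-month interaction, the group term averages the baseline and 3-month differences, (0 + 0.38)/2 = 0.19, and the unadjusted coefficient becomes 0.76 − 0.19 = 0.57. The proportional loss stays roughly the same.

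**5. One fixed baseline-to-6-month change per subject.** A covariate that is constant within subject cancels from within-subject differences, so the interaction coefficient stayed at about 0.76 in every setting. The modelled 6-month difference (group term plus interaction) does not, because the later change is also used to predict baseline. With correlation *r* between the subject's baseline level and fat change:

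difference = 0.76 − (share × 0.76)/2 − *a* × *r* × √0.7

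At *a* = 0.8 and *r* = ±0.3 the last term is ±0.20. For *r* = −0.3 / 0 / +0.3:

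- 25% mediated: formula 0.87 / 0.67 / 0.46; simulated 0.86 / 0.67 / 0.46.
- 50% mediated: formula 0.77 / 0.57 / 0.37; simulated the same.

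Under this coding a participant without a 6-month value has no covariate and leaves the model unless imputed; imputation is planned only for sensitivity analysis. This loss is not quantified here.

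**6. Shared cause only** (true effect zero, no mediation, correlation 0.3, per-visit coding). Shift against FES-RT = *a* × 0.3 × 0.775. For *a* = 0.2 / 0.4 / 0.8 / 1.3 it is 0.05 / 0.09 / 0.19 / 0.30 SD, with simulated rejection rates of 5% / 6% / 11% / 18%, against 5.5–6.4% unadjusted.

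**The case against.** The strongest reply is that DXA has no 3-month value, so the natural reading of a fat term is one change per subject, and then the group-by-6-month coefficient is untouched. That is true for that coefficient in complete data. But the plan commits to neither that coding nor that contrast: its stated test concerns 6-month values, and the modelled 6-month difference does move. Weight is available at all three visits, and a two-visit per-visit fat model shows the same loss.

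A second reply is that the sizes are assumed and may be small. Both comparator arms also do FES leg work; for one of them, Section V says "The arms-only-RT group will also perform the FES-leg strength training protocol as described above", and the wait-list section says the same. This stands. At *a* = 0.2 with 10% mediated, power falls by only 2 to 4 points, and at *a* of 0.2 to 0.4 the false-positive rate stays near nominal. The 50% share and the 11% and 18% rejection rates are extreme cases. At *a* = 0.4 with 25% mediated, the loss is 11 to 18 points.

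Third, the power paragraph lists the primary model without the term. It defers to the later text, which adds it, so it does not supply an unadjusted insulin analysis.

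Fourth, Section VI is unclear on whether the 3-month interaction is in the primary model. The absolute figures depend on that; the direction and roughly the proportional loss do not.

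**Conclusion.** The concern holds. As written, the primary insulin-resistance model conditions on a post-randomisation variable whose fat version Aim 1 expects treatment to change, and the missing coding decides whether the total effect is estimated. With a per-visit term, the coefficient shrinks in proportion to the mediated share: nothing at 0%, about 0.57 SD at 25% and 0.38 SD at 50%, from an assumed 0.76 SD. With a fixed term, the interaction survives in complete data, but the modelled 6-month difference ranged from 0.37 to 0.86 SD in the settings tried.

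The structural point rests on the text alone. The sizes rest on an assumed effect, assumed mediated shares and complete data, and the direction is firmer than the power figures. One of the six outcomes named in Aims 1 to 3 is affected. It should be fixed before analysis.

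**What to change.** In Section VI, take the weight/fat change term out of the primary insulin-resistance model. If adjustment is wanted, use baseline weight or baseline DXA fat.

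Keep the change-adjusted model only as a labelled secondary (mediation) analysis. State there whether the covariate is weight or DXA fat, over what interval the change is taken, whether it has one value per subject or per visit, and that the reading assumes no unmeasured shared causes of fat change and insulin change. Reporting both models is also adequate, provided the one without the change term is named as primary.

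The cost is one or two sentences. Both baseline measures are already collected, so no new data, visits or participants are needed.

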## PARTNERS HUMAN RESEARCH COMMITTEE

### DETAILED PROTOCOL

volunteers with chronic SCI. The main analysis will consist of comparisons across time with injury duration as a covariate.

Given logistical constraints, we began with the assumption that data on 50 acute SCI subjects (out of 60 recruited - a ~15% dropout rate) would be advantageous if that sample size allowed us to find differences that are substantively meaningful. This group would be allocated (randomly; see below) as 40% to FES-RT and 30% to each of wait-list and arms-only-RT. We also checked other total sample sizes and allocation rules (e.g., data from 20 in each group, data from 25 in FES and 15 in each of the other two groups). In addition, 25 individuals with chronic SCI would provide sufficient power to detect meaningful (e.g., >15%) differences between acute and chronic SCI at the same power outlined below.

These calculations were performed assuming an alpha of 0.05 and a correlation between baseline and 6 month measure of about 0.7; unless the correlation was very different from 0.7 (e.g., 0.25), there was little difference in the results. This shows that we will have sufficient power under this plan with a sample size of 50 acute SCI subjects and allocation of 20/15/15. Subjects will be randomized at the ratio of 1.33:1:1 to each of the three groups by a randomization plan constructed by the project statistician. The investigator will have no knowledge of group assignment until the time of subject enrollment. During the study, there can be no blinding of the subject or the investigator, however all measures will be obtained by an individual blind to subject group assignment.

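### One sentence in the primary analysis moves the group by 3-month terms to a secondary analysis, contradicting the stated primary model, and no 6-month contrast is named

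*Combined protocol and SAP*

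**What the plan says.** All references are to the combined protocol and SAP.

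- **Section VI, Power analysis.** The primary model for the acute groups has two group indicators plus "indicators for the 3 month and 6 month time points and interactions between the time points and the group indicator variables". It is a linear mixed model whose only random effect is for subject. The paragraph refers forward to the primary analysis below it. Outcomes are measured at baseline, 3 and 6 months, except visceral adiposity, which is measured at baseline and 6 months only.
- **Section VI, Primary data analysis, predictor list.** FES-RT is the reference group, with an indicator for each of the other two groups, together with "the time at which the outcomes were measured and treatment group by time interactions".
- **Same paragraph, a later sentence.** "In a secondary analysis, we will include interactions terms between the group indicators and the 3 month indicator".
- **Same paragraph, the test.** The question is whether FES-RT has better "values of the outcome variables at 6 months post-baseline". No coefficient or contrast is written down.
- **Section II, Specific Aims.** Aim 1 is "To document changes in body composition (visceral adiposity) and insulin sensitivity" against a wait-list and against arms-only rowing. Its hypothesis adds that "FES-RT will be more effective than arms-only-RT". Aims 2 and 3 are also framed as changes against the same two comparators.

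**The concern.** Terms that are already in the primary model cannot be added to it in a secondary analysis. The last-quoted modelling sentence therefore conflicts with the Power analysis paragraph and with the predictor list in its own paragraph. An analyst who follows the two model descriptions keeps the group by 3-month terms. One who follows the later sentence leaves them out.

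This matters because leaving them out changes what the group by 6-month coefficient means. The model then forces each group difference to be the same at baseline and at 3 months. Any training effect already present at month 3 is absorbed into that common early difference, and part of it is subtracted from the 6-month coefficient.

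How much this matters depends on which quantity is tested, and the plan does not say. The aims point to a difference in change from baseline. The sentence describing the test can be read as a difference in level at 6 months. With both points open, the model and the contrast could be settled after the data are seen.

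**Working it through.** **Inputs from the plan** (section VI, Power analysis): 50 analysed acute subjects, split 20/15/15; alpha 0.05; baseline to 6-month correlation about 0.7; one random effect, for subject. The split reproduces from the 1.33:1:1 ratio: 50 × 1.33/3.33 = 19.97 and 50/3.33 = 15.02.

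**What cannot be reproduced.** The plan says power is sufficient but gives no effect size, SD or power figure for this comparison.

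**Assumptions added here.** Two-sided test; correlation 0.7 for all three visit pairs and equal variances, as a single random intercept implies; complete data; no covariates; normal approximation.

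Let D0, D3 and D6 be the true differences between FES-RT and one comparator at baseline, 3 and 6 months, in SD units. Randomization makes D0 zero in expectation. Let h = 1/20 + 1/15 = 0.1167 and r = 0.7.

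**Step 1: all interactions in the model.** The group by 6-month coefficient estimates D6 − D0, whatever happens at month 3.
SE = √[2(1 − r)h] = √(0.6 × 0.1167) = 0.265.
The effect that gives 80% power is (1.960 + 0.842) × 0.265 = 0.74 SD. It is used below as a yardstick only.

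**Step 2: group by 3-month terms left out.** The common early difference is estimated by the average of the baseline and 3-month differences, so the coefficient estimates D6 − (D0 + D3)/2.
SE = √[1.5(1 − r)h] = √(0.45 × 0.1167) = 0.229.
The ratio of this SE to that in step 1 is √(1.5/2) = 0.866 for any group sizes and any common correlation.

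| Share of the 6-month effect present at month 3 | Coefficient as share of D6 | Power at 0.74 SD |
|---|---|---|
| none | 100% | 90% |
| half | 1 − 0.25 = 75% | 68% |
| all | 1 − 0.50 = 50% | 37% |

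For the last row: 0.5 × 0.741/0.229 = 1.62; 1.62 − 1.96 = −0.34; Φ(−0.34) = 0.37.

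**Step 3: 6-month level difference.** This is the group coefficient plus the group by 6-month coefficient. With complete data it estimates D6 in both models.
SE = √h = 0.342.
Power at 0.74 SD is Φ(0.741/0.342 − 1.96) = Φ(0.21) = 58%. Leaving out the 3-month terms does no harm to this contrast, but it is a less precise test than the change contrast at this correlation.

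**Step 4: which outcomes are affected.** The 3-month question concerns outcomes with three visits: the insulin sensitivity measure, lipids, baroreflex gain and, for the scans obtained before they ended on 1/1/19, echocardiography. Visceral adiposity has no 3-month term. For it, only the choice between change (80%) and level (58%) remains.

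**The case against.** The strongest reply is that the plan has one primary model and one loose sentence. Both places that describe the model in full agree, and the Power analysis paragraph explicitly points forward to the Primary data analysis. The later sentence may mean only that the 3-month contrasts will be reported as secondary. That reading is available, so a reader should not infer that the plan commits to a model without the 3-month terms. What stands is that the sentence speaks of including terms, which is model content, and nothing in the plan rules that reading out.

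A reader might also infer that power is 37%, or that the primary result will be biased. The documents do not support either. The loss needs the terms to be dropped, the group by 6-month coefficient to be the test, and an effect already present at month 3. The plan gives no 3-month effect. Section V allows 2 to 12 weeks of leg strengthening before FES rowing and has arms-only intensity progress over six months, so a complete effect by month 3 is an extreme. With no effect at month 3, the smaller model has more power, not less.

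Finally, a reader might take the correlation remark in the Power analysis, "unless the correlation was very different from 0.7 (e.g., 0.25), there was little difference in the results", as proof that change is the tested quantity, since a level contrast does not depend on that correlation with complete data. The remark fits neither reading cleanly. At a fixed 0.74 SD, power for the change contrast falls from 80% at correlation 0.7 to 58% at 0.5 and 43% at 0.25, and the step to 0.5 is already more than a small difference. The wording of the aims is the better support for change.

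One limit on step 3 is fair. With dropout, the level contrast is not exactly the same in both models. If 60 are randomized 24/18/18 and one-sixth drop out, half before month 3 and half before month 6, the smaller model recovers 97% of the effect when all of it is present at month 3. That is negligible.

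**Conclusion.** The point holds as an inconsistency confined to one sentence, together with an unnamed 6-month contrast. The conflict is certain from the text. Its consequence is conditional: if the sentence is followed as model content and the group by 6-month coefficient is tested, a quarter of the true effect is lost when half of it is present at month 3, and half is lost when all of it is.

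The attenuation follows from the model under equal correlation between visits and complete data. The power figures are illustrative, since they also rest on the assumed 0.74 SD effect and a two-sided test, and they ignore the menstrual-status and weight/fat covariates. The point does not show that the trial is underpowered, and it does not show that a 6-month level comparison would be biased with complete data. It should be corrected because the ambiguity is easy to remove before analysis and hard to defend after it.

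**What to change.** In section VI, state the same primary model in the Power analysis and Primary data analysis paragraphs: group indicators, 3-month and 6-month indicators, and both group by 3-month and group by 6-month interactions. For visceral adiposity, state the two-visit version without 3-month terms.

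Reword the secondary-analysis sentence so that it only reports the 3-month contrasts from that same model.

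Name the primary test as the group by 6-month coefficient, that is, the difference in change from baseline to 6 months, for FES-RT versus wait-list and for FES-RT versus arms-only rowing. This matches the aims and applies to visceral adiposity as well.

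The cost is SAP wording only. No new data, visits or participants are needed.
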